The primary objective of this protocol is to investigate whether IV ghrelin, as compared to placebo, will increase motivation for alcohol reward, as measured by a progressive ratio (PR) schedule paradigm with IV alcohol self-infusion (primary aim). We will also assess a number of secondary aims. Specifically, we will also assess whether IV ghrelin, as compared to placebo, will also alter urges to drink and the subjective response to IV alcohol. Adverse events will also be assessed to ensure the safety of the IV co-administration of ghrelin and alcohol. During an “fMRI/alcohol clamp” session, fMRI will be used to see whether ghrelin affects the activation of the ventral striatum induced by acute IV alcohol administration and the incentive salience of cues associated with alcohol administration.

Study Population. Male and female participants will be non-treatment seeking heavy drinking volunteers.

Design. The study is designed as a within-subject, double-blind, placebo-controlled study of ghrelin. The first visit will be the initial screening visit. The second and third visits will be PR sessions with IV ethanol, during which each participant will also receive IV ghrelin (or matched placebo). The fourth and fifth visits will combine an fMRI session with an ‘alcohol clamp’ session (i.e. a fixed dose of alcohol will be administered) and subjects will participate in a modified version of the monetary incentive delay (MID) task in which they will respond to cues that indicate the opportunity to press a button to gain a reward. On some trials the reward will be points that can be exchanged for snack foods while on other trials the reward will be points that

will determine how much intravenous alcohol a subject will be given during the “alcohol clamp” procedure which will immediately follow the modified MID task. After the modified MID task is complete subjects will have a short break and then begin the alcohol IV infusion.

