- We will determine if ghrelin increases the incentive salience of alcohol predicting cues by using a modified version of the monetary incentive delay (MID) task. In this task subjects will button press to earn credits associated with subsequent alcohol administration, instead of monetary, reward. The MID task has been used extensively in neuroeconomic imaging research and the difference in BOLD signal in the ventral striatum (VS) between anticipation of responding for \$0 and anticipation of responding for \$5 is thought to measure the incentive salience of cues associated with monetary reward.^{140,141} We propose that the difference in striatal BOLD signal between anticipation of responding for a cue predicting no alcohol delivery and cues predicting delivery of alcohol will provide an objective measure of the incentive salience of cues associated with alcohol reward. Our hypothesis is that ghrelin increases the motivational value of alcohol cues. In addition to the VS, other fMRI regions-of-interest (ROI's) for this study are the amygdala, insula and orbitofrontal cortex (OFC), as IV ghrelin has already shown its ability to activate these areas,¹⁴² and all these areas play an important role in the neural systems model of alcoholism.^{20,101,109,112,143}
- In addition to using fMRI to examine ghrelin's effect on the incentive salience of alcohol cues, we will also use fMRI procedures we have developed¹⁴⁴ to examine the effect of ghrelin on the brain's response to IV alcohol. Our previous work has shown that IV

alcohol administration using the “alcohol clamp” procedure (NIAAA protocol 04-AA-0060) results in a robust increase in BOLD signal in the human ventral striatum. Thus, by administering alcohol during functional imaging we should be able to determine if ghrelin enhances the direct pharmacological effect of alcohol on the brain’s reward circuitry.

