perform a MID task during which they can button press to obtain points that determine how much intravenous alcohol or snack food they will be given at the conclusion of the scan. Thus, instead of measuring brain activation while anticipating working for money, we can measure brain activation while anticipating working for alcohol or food. Our group has recently conducted preliminary analysis (PI: [name]; unpublished) of the data obtained from subjects on placebo (n=7); this analysis indicated significantly higher BOLD activation in striatal regions during anticipation of working for alcohol reward under placebo conditions. Preliminary analysis of data from subjects receiving varenicline (n=8) compared to placebo (n=7) show lower

BOLD activation in striatum during anticipation of working for alcohol ($p < 0.01$, uncorrected, $k > 10$) (Figure 6). These results suggest that the Alcohol-MID task can be used to measure motivation or desire for alcohol as well as the effect of a drug on this measure.

[figure not shown]

Figure 6: decreased BOLD activation in striatum (blue region) seen in patients on varenicline compared to placebo during anticipation for alcohol reward in Alcohol-MID task.

Innovation of the study

This protocol is not only a logical ‘next step’ of [name] NIAAA-funded study with ghrelin performed at Brown University, but also there are several new and innovative aspects, i.e. 1) the

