The primary objective of this protocol is to investigate whether ghrelin alters alcohol's pharmacologic effects, including motivation for alcohol reward, as well as subjective measures of craving, and the subjective responses to alcohol in heavy drinkers receiving IV administrations of ghrelin and alcohol.

a. Primary objectives

The primary measure of this study will be the breakpoint, which is the schedule (number of button presses) at which the individual stops to work for more alcohol.

b. Secondary objectives

Secondarily, the BrAC exposure measures will also be determined, that is the highest (max) BrAC, average BrAC and the area under the BrAC-time curve determined for each subject. Urge to drink and alcohol sensitivity will be measured during the PR session. Adverse events will also be assessed in order to assess the safety of the IV co-administration of ghrelin and alcohol. Also, during the "fMRI/alcohol clamp" session, fMRI will be used to see whether ghrelin affects the activation of the ventral striatum (VS) in anticipation to work for alcohol reward and the incentive salience of cues in subjects who will subsequently receive IV alcohol administration. In

addition to the VS, other fMRI ROI's are the amygdala, insula and OFC. Adverse events will also be assessed during the fMRI/alcohol clamp sessions.

Furthermore, an additional secondary aim will be an exploratory analysis of the role of genetic polymorphisms of both ghrelin and ghrelin receptor genes – detailed in page 14 – as possible moderators of ghrelin's effects on the primary aim ('breakpoint', i.e. number of button presses in the IV alcohol PR procedure).

3. Subjects:

a. Description of study populations

Male and female adults will be eligible to participate in this study. Participants will be non-treatment seeking heavy drinking volunteers. Our goal is to screen 124 subjects and recruit 62 individuals. Assuming a 20% drop-out rate, we will reach 50 completers.

b. Inclusion criteria

1. Male and female participants between 21-60 years of age.
2. Good health as determined by medical history, physical exam, ECG and lab tests.
3. Creatinine \leq 2 mg/dl.

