Outcome data will be examined for homogeneity of variance, and if necessary transformed to meet this criterion. Most of the analyses will consist of repeated measures ANCOVAs to accommodate dependent measures assessed at multiple time points. When the dependent measure is just assessed once then a regular ANCOVA will be used. We will examine medication main effects across several different dependent measures.

Criteria for significance

A probability level of 0.05 or lower will be considered significant.

2. Power analysis

Power analysis

A generic calculation of power for a two-means comparison to detect an effect size of Cohen's $f \geq 0.4$ (large effect size) with a sample size of 50 yields a power estimate ≥ 0.80 at alpha=0.05. The relative effect size chosen (“large” effect size) for the power calculation is based on the observation that laboratory studies typically yield larger effect sizes than clinical trials, including, for example, our recent (unpublished; PI: [name]) human lab studies using the

IV Alcohol PR procedure, described above and representing the study our primary aim (number of button presses) is based upon.

Furthermore, the sample proposed here provides sufficient power (power estimate ≥ 0.80 at alpha=0.05) to detect ghrelin's effects on fMRI BOLD activation in the VS, consistent with the unpublished data (PI: [name]; data already mentioned above) with varenicline (n = 8) vs. placebo (n = 7) indicating significantly higher BOLD activation in the varenicline group.

Accrual number request, taking into account screening/ dropouts

In the Brown University study with IV ghrelin, inclusionary/exclusionary criteria were similar and about 50% of the subjects screened were eligible and randomized. Consistent with other human laboratory studies with a similar study length, we also expect that a number up to 20% will not complete the study. Therefore, we anticipate a number-needed-to-screen of 124 subjects, with 62 being randomized and 50 completers.

11. Human Subjects Protection

a. Subject selection

Adults who fulfill the qualification criteria will be included, regardless of race, ethnicity, sex, or religious affiliation.

b. Justification for inclusion of children

Children will not be included because the study proposed involves the administration of alcohol. It is illegal to give alcohol to individuals below 21 years of age.

c. Justification for inclusion or exclusion of other vulnerable subjects

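### Is the stated fMRI power of at least 0.80 undermined because the varenicline pilot is described in opposite directions and no BOLD effect size is given?

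*Combined protocol and SAP*

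**What the plan says.** Section 10, Power analysis, makes two statements. The first is a generic two-means calculation: Cohen's f of at least 0.4, 50 participants, alpha 0.05, power of at least 0.80. Its effect size is justified by laboratory studies in general, with the IV alcohol progressive ratio (PR) work as the example.

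The second concerns imaging: "Furthermore, the sample proposed here provides sufficient power (power estimate ≥ 0.80 at alpha=0.05") to detect ghrelin's effect on VS BOLD. This is said to be consistent with unpublished varenicline data already mentioned, "indicating significantly higher BOLD activation in the varenicline group".

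Those data appear in the introduction, under fMRI/alcohol clamp: "Preliminary analysis of data from subjects receiving varenicline (n=8) compared to placebo (n=7) show lower" "BOLD activation in striatum during anticipation of working for alcohol", at p < 0.01 uncorrected with k > 10. The Figure 6 legend agrees: "decreased BOLD activation in striatum (blue region) seen in patients on varenicline compared to placebo".

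Two VS questions are described. Section 2b names "activation of the ventral striatum (VS) in anticipation to work for alcohol reward". The Precis says that "fMRI will be used to see whether ghrelin affects the activation of the ventral striatum induced by acute IV alcohol administration", and the introduction expects imaging during the infusion to "determine if ghrelin enhances the direct pharmacological effect of alcohol on the" brain's reward circuitry. Sections 2b and 9b both class the fMRI measures as secondary.

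**The concern.** The group sizes match and Section 10 points back to data already described, so the two places report one dataset in opposite directions. That dataset is the only evidence cited for the fMRI power.

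It is also weak evidence. It concerns another drug and compares separate groups, whereas this trial compares each participant with himself or herself. It is reported only as passing an uncorrected threshold, with no mean, SD or effect size. It covers the striatum generally and the anticipation phase only, and no pilot is cited for the response to infused alcohol.

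A reader therefore cannot tell how large a VS effect the trial could detect. The risk is that a null VS result is read as coming from a test whose power had been demonstrated.

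**Working it through.** **Inputs.** 50 completers (Sections 3a and 10; 62 × 0.8 = 49.6), alpha 0.05 and f = 0.4 (Section 10), within-subject design (Section 4a), pilot groups of 8 and 7. Two-sided testing is assumed, because Section 10 does not state sidedness. The between-session correlation r is not given, so a range is shown.

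**1. The generic figure.** For two means d = 2f = 0.8. With 25 per group the noncentrality is 0.8 × √(25 × 25/50) = 2.83.
- Normal approximation: Φ(2.83 − 1.96) = 0.807.
- Noncentral t, 48 df: 0.791.
- Taking 0.4 instead as the standardised within-person difference dz, paired with n = 50: noncentrality 0.4 × √50 = 2.83, 49 df, power 0.792.

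The stated 0.80 is reproduced to within one point. The exact t versions fall just under it.

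**2. The same effect size in the trial's own design.** If d = 0.8 is a mean difference in SD units, dz = d/√(2(1 − r)), tested as pairs with n = 50.

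| r (assumed) | dz | Power |
|---|---|---|
| 0 | 0.566 | 0.975 |
| 0.3 | 0.676 | 0.997 |
| 0.5 | 0.800 | > 0.999 |

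**3. The fMRI figure.** It cannot be reproduced directly, because no BOLD effect size is printed. The paired noncentral t (n = 50, two-sided 0.05) shows what it would require.

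| dz (assumed) | Power |
|---|---|
| 0.2 | 0.284 |
| 0.3 | 0.548 |
| 0.4 | 0.792 |
| 0.5 | 0.934 |

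Power reaches 80% at dz = 0.404. As a mean difference this is 0.404 × √(2(1 − r)): 0.57 SD at r = 0, 0.40 SD at r = 0.5 and 0.31 SD at r = 0.7.

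**4. Does the sign matter?** Two-sided power at dz = −0.5 equals that at +0.5, namely 0.934. Swapping higher for lower changes no power figure.

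**5. Could the pilot supply an effect size?** If p < 0.01 came from an ordinary two-sample t test on 13 df, |d| would be at least 3.012 × √(1/8 + 1/7) = 1.56 (two-sided), or 2.650 × 0.518 = 1.37 (one-sided). A value selected by an uncorrected threshold, for another drug and between groups, is not usable for planning. The pilot therefore neither establishes nor contradicts power of 0.80.

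**6. A likely source of the slip.** Just before the varenicline comparison, the introduction reports significantly higher striatal activation in the seven placebo participants alone while they anticipated working for alcohol. The wording in Section 10 may have been carried over from there. This is an inference.

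**The case for a change.** The strongest case for acting is that the sponsor chose to state a numerical power for this endpoint. The claim follows the generic calculation as a separate sentence tied to the varenicline data, and the generic f is defended from PR work, not imaging. If the true dz were 0.2 to 0.3, a real effect would be missed about 72% to 45% of the time (1 − 0.284 and 1 − 0.548). The study presents ghrelin's effect on the brain's response to alcohol as new information, so a null result there would attract attention. Correction would cost only a sentence or two.

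Part of this stands. The two descriptions do conflict, and the effect size assumed for the VS is not written down. The remainder does not carry as far:

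- The values of 0.2 to 0.3 have no source in the documents. The only planning effect size in the section is f = 0.4. The fMRI sentence quotes the same power and alpha and calls itself consistent with the pilot, not calculated from it. Reading it as an extension of the generic calculation is fair, although the basis is thin.
- The contrast is less ambiguous than it looks. Section 2b names anticipation and the pilot measured anticipation.
- A more exact replacement is not readily available. A detectable dz of 0.40 belongs to a paired t-test, whereas Section 10 plans repeated measures ANCOVA, and the reward task is run before drug, during ghrelin or placebo, and during the alcohol clamp. Nor could the protocol safely say that no ghrelin BOLD estimate exists. The introduction cites an imaging study in which IV ghrelin activated the amygdala, insula and orbitofrontal cortex, and what it reports for the VS cannot be seen from here.

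**Conclusion.** No change to the plan follows. The conflict over the pilot's direction is a clerical slip. The introduction and the Figure 6 legend agree with each other, and anyone with the pilot data can settle which description is right. The missing VS effect size is an unwritten assumption for a secondary outcome.

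Neither bears on a result. Two-sided power ignores the sign, N = 50 is argued from the generic calculation, and the planned analysis does not use the pilot. The documents do not show fMRI power below 0.80. Under a simple paired test it is about 0.80 at dz = 0.40, and at least 0.975 if f = 0.4 is read as d = 0.8 with a non-negative correlation between sessions. These figures assume two-sided 0.05, 50 complete pairs and one VS contrast.

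A null VS finding should be judged from its confidence interval, which the analyst will have whatever the power sentence says.

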[name], Pharm. D., Ph.D., is a tenured full professor in the College of Pharmacy, University of Rhode Island (URI) and adjunct professor of Medicine at Brown University Medical School. Her area of specialty is clinical pharmacology in diabetes and transplantation; she also conducts clinical pharmacokinetics research at Rhode Island Hospital, Providence, RI. [name] is also a member of the IRB at URI. [name] is the Co-PI, together with [name], of the multiple-PI UH2/UH3 grant funded by NCATS. Her laboratory at URI will receive samples that are de-identified from this study. She or her lab personnel will not have any means of linking the study codes to subjects' personal information. She will not obtain consent for this study.

12. Anticipated Benefit

This study does not offer direct benefit to participants but is likely to yield generalizable knowledge about the possible role of ghrelin in alcohol-related behaviors (e.g. drinking, craving,

sensitivity). This will markedly facilitate the identification of a novel neuropharmacological target, thus facilitating the development of novel alcoholism treatments.

13. Classification of risk

Overall risk and discomfort in this study is “more than minimal”. The increase over minimal risk, discomfort is minor, and every precaution and protection to minimize any risks will be taken as described in a previous section. This level is justified, because it will markedly facilitate medication development for alcoholism, and thus contribute to addressing major unmet medical needs. As such, the benefit:risk ratio of the proposed study is favorable.

14. Consent documents and process

a. Designation of those obtaining consent

Study investigators designated as able to obtain consent in section ‘11f’ above, will obtain informed consent for this protocol.

b. Consent procedures

At Visit 1 (Screening), subjects are screened throughout the NIAAA Screening protocol 98-AA-0009 (PI: [name].) or 14-AA-0181 after consenting participants with an already IRB-approved consent form, specific for the 98-AA-0009 or 14-AA-0181 protocol.

Eligible subjects are scheduled for Visit 2; the study-specific consent form for ghrelin is obtained at Visit 2 before starting the other procedures outlined for Visit 2. Nonetheless, at Visit 1, if all information necessary to determine eligibility is obtained and the participant is still in our Clinic, then the ghrelin-specific consent form can be obtained at the end of Visit 1 (although we predict this will be not a frequent scenario). In summary, the ghrelin-specific consent form will be typically obtained at Visit 2, and occasionally at the end of the Visit 1. Participants who might be eligible at the end of Visit 1 (but we will make clear that their eligibility will have to be confirmed) will be allowed to take the consent document home before Visit 2 is scheduled. As such, potential participants have the option to read the consent home, call us with questions, and consult (if they want) family members and/or their private health care professional. The ghrelin-specific consent form will be obtained before starting the procedures scheduled for Visit 2, and all procedures of Visit 2 will always take place on a different subsequent day after Visit 1.

All participants will receive a verbal explanation in terms suited to their comprehension of the purposes, procedures and potential risks of the study and of their rights as research participants. Participants will have the opportunity to carefully review the written consent form and ask questions regarding this study prior to signing. Participants will be asked to sign and date the informed consent. A copy of the signed and dated consent will be provided to each participant. In regards to consenting participants who might be impaired, our standard procedure is for the nurses to do a breathalyzer test upon arrival (covered generally under the standard hospital consent that all subjects admitted to the NIH Clinical Center sign when they check in at admissions). If the results is >0.03 , then the subject is informed that we cannot proceed, and they are given the option of waiting until their level falls below 0.02 and/or sending them back in a cab. If the reading is >0.08 , we strongly encourage them to stay at least until they drop below the legal limit (and if participants came by car and don't want to wait until < 0.08 , then the NIH police is notified, as already specified in the consent). If the reading is ≤ 0.03 , we let the subject know that we will need to wait 1-2 hours to ensure their readings are back to zero before they can sign the consent form and proceed.

After negative breathalyzer is obtained, the consent process will take place and then study procedures will start. The NIH CC nursing staff in charge of the participant will be required to first complete and sign a 2-item checklist [*i.e.: a) ask to the participant whether or not they have been consented; and b) verify consent was signed*] before study procedures take place at the time of the admission (Visit 1). As part of the consent procedure, participants' ability to understand the consent will be evaluated using the '*NIDA/NIAAA Evaluation of Potential Research Participants' Ability to Consent*'.

c. Consent documents

The consent form attached in the Appendix contains all required elements. The original consent is filed with their NIH medical record and a digital copy is uploaded into the CRIS system. A copy of the signed consent is also made for the subject's CRF binder for regulatory purposes.

Data and Safety monitoring

d. Data and Safety monitor

Data and safety monitoring commensurate with the degree of risk involved in participation in a small, single-site trial like the present one and will be performed by an independent safety monitor (ISM).

e. Data and safety monitoring plan

The ISM is a physician with relevant expertise, whose primary responsibility is to provide independent safety monitoring in a timely fashion. To ensure expertise in clinical addiction research as well as independence, the ISM for the current study will be a physician from a different Section of NIAAA. The ISM responsibilities will be assumed by [name]., NIAAA or [name]. NIAAA.

The ISM evaluation includes the progress of the research study as documented in the "ISM Monitoring Report and Log", data quality from review of adverse events, lab data and relevant clinical data collected immediately after they occur or are reported, with follow-up through resolution, and participant accrual in the Screening and Enrollment Log. The ISM reviews on an ongoing basis individual and cumulative participant data, and makes recommendations regarding the safe continuation of the study, or its termination. The ISM may break the study blind if needed. Weekly safety data monitoring reports are generated by NIAAA Staff Scientist and sent via encrypted email to the MAI, ISM and PI for review and consideration. Appropriate action is then conveyed to the research team.

The ISM will submit their review findings on the "Independent Safety Monitoring Report and Log" (stored in regulatory binder) for the PI and MAI to review. The PI will submit all findings from this review at the time of continuing review and/or in the case of a PR report the timing of which is in compliance with OHSRP guidelines.

Adverse Event reporting and/or Problem Reporting will be performed consistent with current OHSRP and NIH SOP Guidelines including; report submission in PTMS for OCD and IRB review, email notification to the study sponsor if this is a separate individual from the PI, hard copy notification in triplicate via Fed Ex/U.S. Mail to the FDA.

Criteria for stopping the study or suspending enrollment or procedures

The study will be terminated if more than five individuals experience serious adverse events (SAEs) related to the study drug [> 5 SAEs].

There is no plan at this stage to conduct an interim analysis.

f. Criteria for suspending study procedures on an individual basis: Administration of study medication or alcohol will be suspended on a case- by-case basis as per the PI and MAI request in accordance with the following criteria

Checklist:

- Clinically significant findings including changes in mood or behavior such as aggression, agitation, depression or suicidal ideation or suicidal behavior.
- Changes in concomitant medications that may interact with study medication or alcohol.
- At the discretion of the Principal Investigator (PI) and Medical Investigator, based on adverse event (AE) severity
- Non-compliance with protocol procedures or investigator request(s)
- Patient request
- Equipment failure

Please see also “Criteria for individual subject withdrawal”, Section 8. **Subject Safety monitoring**

15. Clinical Monitoring/Quality Assurance

Quality assurance will be monitored by the PI and research team and the NIMH/NIAAA/NIDA Combined Monitoring Plan, Intramural Research Program Auditing Committee (IRPAC) (Please see Appendix (E) – Standard Operating Procedures for the Intramural NIMH, NIAAA and NIDA Combined Monitoring Plan) coordinated by the Offices of the Clinical Director at NIMH, NIAAA and NIDA. The NIMH/NIAAA/NIDA Combined Monitoring Plan, Intramural Research Program Auditing Committee (IRPAC) monitors intramural research studies to ensure compliance with GCP, organizational policies and applicable federal, state and local laws and the reliability of study data.

a. Quality assurance monitor

- Quality assurance (QA) will be performed by the PI, as well as by an independent QA monitor, which according to established practice is considered sufficient for small, single-site trials, like the present project. The QA monitor for this study will have considerable expertise in clinical trials in alcohol dependence, and will have completed training in Clinical Research Monitoring and GCP Compliance.

b. Quality assurance plan

- All participants' data and binders will be reviewed on a monthly basis.

16. Adverse event and unanticipated problem reporting

Adverse events, protocol deviations, unanticipated problems (UP), Unanticipated Adverse Device Effects (UADEs), serious adverse events are defined as described in NIH HRPP SOP 16 (“Reporting Requirements for Unanticipated Problems, Adverse Events and Protocol Deviations.”). The Principal Investigator is responsible for detecting, documenting, and reporting unanticipated problems, adverse events (AEs), including serious adverse events (SAEs), and deviations in accordance with NIH policy, IRB requirements, and federal regulations. Relatedness to the research of all serious adverse events will be determined by the PI in consultation with the CD.

Serious unanticipated problems and serious protocol deviations will be reported to the IRB and CD as soon as possible and in writing on the Problem Report Form not more than 7 days after the PI first learns of the event. Not serious unanticipated problems and not serious deviations will be reported to the IRB and CD as soon as possible and in writing on the Problem Report Form not more than 14 days after the PI first learns of the event. Deaths will be reported to the Clinical Director within 7 days after the PI first learns of the event. All adverse events, deviations, and unanticipated problems will be summarized and reported at the time of Continuing Review.

17. Alternatives to participation or Alternative therapies

To be eligible for this study, subjects must not be seeking help for drinking problems. Those who are seeking help for a drinking problem will be referred to standard therapy for heavy drinking and will not be allowed to participate in this study.

18. Confidentiality

This protocol is covered by a Certificate of Confidentiality (CoC) issued by the US Department of Health and Human Services. Strict subject confidentiality will be maintained throughout the study. Confidentiality and information technology standards are in place at the NIAAA/LCTS intramural program to protect electronic repositories of patient data as well as other clinical patient related material. It is reasonably expected that these safeguards will protect participants' medical and personal health information, ensuring their privacy.

Information obtained in the course of being screened for or participating in this protocol will become part of the patient's NIH medical record. This includes potentially sensitive information, such as urine tests positive for illicit drugs. Access to this information may be requested by third parties. Such access will not be granted without the explicit, written consent of the subjects.

Samples and data will be stored using codes that we assign. Data will be kept in password protected computers. Samples will be kept in locked storage. Only study personnel will have access to the samples and data.

20. Conflict of Interest

a. Distribution of NIH Guidelines

NIH guidelines on conflict of interest have been distributed to all investigators.

b. Conflict of interest

There are no conflicts-of-interest to report.

c. Role of a commercial company or sponsor

There is no drug company involved.

21. Technology Transfer

No technology will be subject to transfer to agencies outside the US Government.

22. Compensation

Volunteers will be compensated for time and research-related inconveniences, to the extent to which they complete them, as follows:

Visit #	Compensation
Visit 2 (alcohol PR)	\$250
Visit 3 (alcohol PR)	\$250
Visit 4 (fMRI/alcohol clamp)	\$250
Visit 5 (fMRI/alcohol clamp)	\$250
Visit 6 (Follow-up: \$25 + bonus for completing all parts of the study: \$100)	\$125
TOTAL	\$1,125

Compensation will be prorated for parts completed if subjects do not complete the study. If needed, subjects will be provided with a taxi paid for by NIH.

Visit 1 (Screening) is done under a separate NIAAA protocol, i.e. the NIAAA Screening Protocol 98-AA-0009, (PI: [name].) or 14-AA-0181. The 98-AA-0009 protocol has been routinely used in the NIAAA Clinical Program for several years to screen non-treatment seeking individuals who are then enrolled - pending on their eligibility - in more specific studies, such as this proposed study with ghrelin. Therefore, all human lab studies with non-treatment populations performed in the NIAAA Clinical Program enroll participants who were first screened via the 98-AA-0009 protocol or the 14-AA-0181.

22. References

